- d A QuantiFERON TB/T-spot or local equivalent will be performed. For the purposes of this study. Additional TB tests could be performed during the course of the study at the discretion of the investigator and according to local practice.
- ^e Chest radiograph will include anterior/posterior or posterior/anterior and lateral views. Historical films obtained or formal reports signed off by radiologist in the 3 months prior to screening are acceptable. Chest X-ray may be substituted by a chest CT or chest MRI, if available within 3 months prior to screening.
- Only for subjects with a positive tuberculosis test (ie, positive or indeterminate QuantiFERON, positive PPD).
- Pharmacokinetic sample will be collected as close to the nominal time points as possible. Study centers should strictly adhere to the tolerance windows outlined in the table below for week 28 through week 30 PK endpoint sample collection.
- h Pharmacokinetic and antidrug antibody samples should be drawn prior to investigational product administration at dosing visits (except 1 hour post week 28 dose pharmacokinetic sample).
- ABP 501 or adalimumab will be administered after all other procedures are completed for each visit. If the subject presents with an infection/adverse event at the dosing visit(s), the administration of investigational product may be delayed up to 5 days. In the case of delayed or missed dose, subsequent doses should be administered according to the original schedule (ie, at the planned time point relative to first dose/day 1). A minimum of 7 days must elapse between administrations of 2 doses.
- Subjects achieving less than PASI 50 response at week 12 visit will be considered non-responders and will be discontinued from the study at week 12. Subjects unable to complete the week 12 visit will be discontinued from the study. These subjects will be asked to complete an End of Study Visit procedures.

Table 1-2. Tolerance Windows for Pharmacokinetic Endpoint Sample Collection

Study Visit	Tolerance Windows ^a	
Week 28 predose	Within 3 hours prior to week 28 investigational product administration	
1 hour post week 28 dose	± 15 minutes	
1 day post week 28 dose	± 5 hours	
3 days post week 28 dose	± 6 hours	
4 days post week 28 dose	± 6 hours	
7 days post week 28 dose	± 6 hours	
11 days post week 28 dose	± 24 hours	
14 days post week 28 dose	± 48 hours	

PK = pharmacokinetic(s).

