Developing antibody incidence during the Post-randomization Period is defined as the number of subjects in the Safety Analysis Set (SAS) who have a positive result post randomization and have never tested positive (i.e., negative or no results) prior to the first dose of post-randomization IP divided by the number of subjects in the SAS who have at least a result post randomization.

End of Study (EOS) Date

The EOS date is the date recorded on the End of Study page of the CRF.

First Dose Date

It is defined as the date the subject received the first dose of IP.

First Post-randomization Dose Date

It is defined as the date the subject received the first post-randomization dose of IP.

Last Dose Date

It is defined as the date the subject received the last dose of IP.

Last Observation Carried Forward (LOCF)

Protocol Number: 20200497

Date: 10FEB2023 Page 14 of 36

A method of imputation where missing post-baseline data will be imputed by carrying forward the last non-missing post-baseline value for that endpoint. Baseline values will not be carried forward.

Neutralizing ADA Negative Subgroup

Defined as subjects in the subset of Safety Analysis Set (SAS) who have never tested positive (i.e. tested negative or no results) prior to the first dose of post-randomization IP, have at least one neutralizing ADA result post-randomization, and all available post-randomization neutralizing ADA results are negative.

Non Responder Imputation (NRI)

A method of imputation where a subject with missing post-baseline binary response data will be imputed as a non-responder, regardless of the reasons for missing data.

Study Analysis Visit

If more than one actual visit (including the unscheduled visits) falls within the same defined window, the visit closest to the target day with non-missing data will be considered for analysis. If two actual visit dates are at the same distance from the target day, the later visit with non-missing data will be considered for analysis.

For Efficacy, Vital, Safety Lab & PK

					Endpoint	
Study Analysis Visit	Target Day	Study Day	Interval (days)	Efficacy	Vital & Safety Labª	PK
Baseline ^b	1	≤1	NA	Х	Х	Х
Week 2	8	2-21	20		X	
Week 6	36	22-56	35	Χ	X	Χ
Week 12 ^b	78	57-91	35	Χ	X	Χ
Week 16	106	92-119	28	Χ	X	Χ
Week 20	134	120-161	42	Χ	X	Χ
Week 28	190	162-196	35		X	Χ
Week 30	14 days post week 28 dose	197-210	14	Х	Х	
Week 32	218	≥211	NA		Χ	

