^a Safety lab is not scheduled at week 2 and week 16. Laboratory parameters assessment will not be included at these two visits in the output tables.

^b If a subject has laboratory measurements on the same day as the first dose date at week 1/Day 1 or week 12 but at a time after the first dose of IP at week 1/Day 1 or week 12, respectively is administered, the laboratory measurements will not be defined as baseline or week 12, but will be included in consideration for week 6 or 20 measurements, respectively.

Protocol Number: 20200497

Date: 10FEB2023 Page 15 of 36

PK concentrations between Week 28 – Week 30 are summarized by nominal study visit per the following table as listed in the protocol:

Tolerance Windows for Pharmacokinetic Endpoint Sample Collection

Study Visit	Tolerance Windows ^a
Week 28 predose	Within 3 hours prior to week 28 investigational product administration
1 hour post week 28 dose	±15 minutes
1 day post week 28 dose	±5 hours
3 days post week 28 dose	±6 hours
4 days post week 28 dose	±6 hours
7 days post week 28 dose	±6 hours
11 days post week 28 dose	±24 hours
14 days post week 28 dose	±48 hours

^a The week 28 visit and dose should be performed with a window of \pm 3 days. Subsequent visits are done in relation to the actual week 28 investigational product dose date (eg, for the 3 days post week 28 dose timepoint, the PK sample should be collected 3 days after the actual week 28 dose, with a collection window of \pm 6 hours). PK: pharmacokinetic(s)

For ADA

Study Analysis Visit	Target Day	Study Day
Baseline	1	<=1
Week 6	36	<=56
Week 12	78	<=91
Week 16	106	<=119
Week 20	134	<=161
Week 28	190	<=196
Week 30	14 days post week 28 dose	<=210
Week 32	218	<=EOS Visit Date

Study Day

Study day is defined as the number of days from Study Day 1.

Before Study Day 1: Study Day = (Date of assessment – Date of Study Day 1)

Protocol Number: 20200497

Date: 10FEB2023 Page 16 of 36

On or After Study Day 1: Study Day = (Date of assessment – Date of Study Day 1) +1

Therefore, the day prior to Study Day 1 is -1.

Study Day 1

Study day 1 is defined as the first day of IP the subject received (see definition of first

dose date).

Study Period

The following definitions will be used for PK, safety and efficacy analyses.

Lead-in Period

It is defined as the time period from the first dose of IP the subject received (see

definition of first dose date for the subject) until prior to the first post-randomization dose

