for subjects who are randomized and treated post-randomization, or to the EOS visit for

subjects not randomized or for subjects who were randomized but not treated post-

randomization.

Post-randomization Period

For subjects who are randomized and treated post-randomization, it is defined as the

time period from the first post-randomization dose to the EOS visit.

Study Randomization

Study randomization is defined as when subject receives a random treatment allocation

via the IXRS system.

Total IP Exposure Duration

The total IP exposure duration for the subject (in weeks) for each study period (Lead-in

Period, Post-randomization Period) will be derived as: (the period end date - the period

start date+1)/7. The Lead-in Period end date for the subjects who are randomized and

treated post-randomization is the date of the first IP post randomization -1.

Transient ADA

A transient ADA result during the Lead-in Period is defined as a positive antibody result

post-baseline (including unscheduled visits) during the Lead-in Period with a negative or

no antibody result at baseline and a negative result at the subject's last visit tested within

the Lead-in Period.

Protocol Number: 20200497

Date: 10FEB2023 Page 17 of 36

A transient ADA result during the Post-randomization Period is defined as a positive antibody result post-randomization (including unscheduled visits) during the Post-randomization Period with negative or no antibody results prior to the first dose of post-randomization IP and a negative result at the subject's last visit tested within the Post-randomization Period.

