8.3 Handling of Missing, Below LLOQ and Incomplete Data

Missing PK concentration data and endpoints will not be imputed.

For the purpose of calculating AUC $_{tau}$, concentrations that are below the LLOQ after t_{max} will be excluded; values less than the LLOQ that are encountered prior to t_{max} will be set to zero and included. Individual AUC $_{tau}$ will be flagged if less than 2 post t_{max} concentration values are reported or less than 2 post t_{max} concentration values are above LLOQ.

For summary statistics and linear plots for the PK concentrations, concentration values < LLOQ will be set to zero. For log-linear plots, concentration values below LLOQ will not be displayed.

The handling of missing values for efficacy endpoints are detailed in Section 9.6.

Missing safety and ADA endpoints will not be imputed.

Imputation for Partial or Missing Dates

If dates are missing or incomplete for an AE (including deaths) or concomitant medication, the following algorithm will be used for imputation:

Stop Date	
	Stop Date

Protocol Number: 20200497

Date: 10FEB2023 Page 23 of 36

		Complete: yyyymmdd		Partial: yyyymm		Partial: yyyy		Missin g
		<1st dose	≥1st dose	<1st dose yyyym m	≥1st dose yyyymm	<1st dose yyyy	≥1st dose yyyy	
Partial: yyyym m	= 1st dose yyyymm	2	1	n/a	1	n/a	1	1
	≠ 1st dose yyyymm		2	2	2	2	2	2
Partial: yyyy	= 1st dose yyyy	- 3	1	3	1	n/a	1	1
	≠ 1st dose yyyy		3	Č	3	3	3	3
Missing		4	1	4	1	4	1	1

- 1 = Impute as the date of first dose
- 2 = Impute as the first of the month
- 3 = Impute as January 1 of the year
- 4 = Impute as January 1 of the stop year

Note: If the start date imputation leads to a start date that is after the stop date, then there is a data error and do not impute the start date.

Imputation rules for partial or missing stop dates:

- 1. Initial imputation
 - a. For partial stop date "mmyyyy", impute the last of the month.
 - b. For partial stop date "yyyy", impute December 31 of the year.
 - c. For completely missing stop date, do not impute.
- 2. If the stop date imputation leads to a stop date that is after the death date, then impute the stop date as the death date.
- 3. If the stop date imputation leads to a stop date that is before the start date, then there is a data error and do not impute the stop date.

Imputation rules for partial or missing death dates:

- 1. If death year and month are available but day is missing:

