9.7.6 Antibody Formation

The number and percent of subjects developing binding or neutralizing ADA will be tabulated descriptively by treatment group and visit in the SAS for the Postrandomization Period and in the LTS for the Lead-in Period.

The incidence of transient antibody will also be summarized for each study period.

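### The ADA visit windows in SAP 5.1 have upper limits only, so under the closest-to-target rule a missing post-randomization sample is filled by an earlier one, contrary to SAP 8.3

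*SAP*

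**What the plan says.** SAP 5.1 (Study Analysis Visit) has one selection rule followed by two window tables.

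- **Rule.** When more than one visit, unscheduled visits included, "falls within the same defined window, the visit closest to the target day with non-missing data will be considered for analysis". Ties go to the later visit. ADA is not exempted, and SAP 9.1 applies the derived visit to every by-visit summary unless noted otherwise.
- **Efficacy, vital signs, laboratory and PK table.** The windows have both bounds and do not overlap, for example week 16 = days 92 to 119 and week 20 = days 120 to 161.
- **ADA table.** It has target days and upper limits only: week 6 up to day 56, week 12 up to 91, week 16 up to 119, week 20 up to 161, week 28 up to 196, week 30 up to 210, and week 32 "<=EOS Visit Date".

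SAP 8.3 states: "Missing safety and ADA endpoints will not be imputed". Under SAP 9.7.6 the number and percentage developing binding or neutralizing ADA are "tabulated descriptively by treatment group and visit in the SAS for the Postrandomization Period", with a corresponding lead-in table. SAP 5.1 defines the Post-randomization Period, for subjects treated after randomization, as the "time period from the first post-randomization dose to the EOS visit".

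**The concern.** Without a lower bound, each ADA sample lies in its own window and in every later one. The closest-to-target rule then always finds a candidate for a later visit, even when no sample was taken there. An old result would appear in the table under a later week, with nothing to mark it as old. That is last observation carried forward in effect. SAP 5.1 defines that method separately, and SAP 9.6 invokes it for PASI and BSA, not for ADA.

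Immunogenicity after switching is a listed secondary endpoint, and the by-visit table is where a reader would look for when antibodies appear. As the text stands, two programmers could produce different tables from it: one carrying results forward, the other leaving gaps or counting cumulatively.

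**Working it through.** **1. The plan's own figures.** Target day = 7 × (week − 1) + 1 gives 36, 78, 106, 134, 190 and 218 for weeks 6, 12, 16, 20, 28 and 32, all as printed in the ADA table. Week 30 is set at 14 days after the week 28 dose, so day 204 if that dose is on day 190 (assumed below). In the two-sided table, upper − lower + 1 gives 20, 35, 35, 28, 42, 35 and 14 days for weeks 2 to 30, also as printed. That table is internally consistent.

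**2. Complete samples.** With every sample on its target day, each visit selects its own sample, with or without lower bounds. The problem arises only when a sample is missing.

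**3. Week 20 missing, post-randomization samples only.** The week 20 window is day 161 or earlier. The week 16 sample (day 106) is inside it, at a distance of |106 − 134| = 28 days, and is the only post-randomization candidate. It is reported as week 20. With a lower bound of day 120, week 20 stays empty.

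**4. Last sample at week 16, post-randomization samples only.**

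| Visit | Target day | Upper limit | Distance of day 106 sample | As written | With lower bounds |
|---|---|---|---|---|---|
| Week 20 | 134 | 161 | 28 | week 16 result | missing |
| Week 28 | 190 | 196 | 84 | week 16 result | missing |
| Week 30 | 204 | 210 | 98 | week 16 result | missing |
| Week 32 | 218 | EOS date | 112 | week 16 result | missing |

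An early-termination sample behaves in the same way. If a subject's only post-randomization sample is an EOS sample on day 92, it satisfies all five limits from week 16 to week 32 and is shown five times. With lower bounds it appears at week 16 only.

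**5. The cumulative reading.** Suppose a subject is positive on day 106 and negative on day 134. For week 20 the rule compares distances of 28 and 0 and keeps the negative. A count of subjects positive at any time through week 20 should include this subject. SAP 5.1 defines transient ADA, so the plan itself foresees such sequences. The rule therefore does not give cumulative incidence either.

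**6. What does not use these windows.** Overall developing-ADA incidence uses any positive result in the period. Transient ADA uses the last visit tested. The neutralizing-ADA-negative subgroup requires that "all available post-randomization neutralizing ADA results are negative". The primary PK analysis uses the week 28 to 30 profile. None of these changes.

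**The case against.** The best defence is that upper limits alone, placed directly after a fully bounded table and ending at the EOS date, look deliberate: they suit a count of subjects who have developed ADA through each week. On that reading nothing is imputed and SAP 8.3 is not contradicted. This is plausible, but the SAP never says it. The ADA table also keeps a target-day column, which a cumulative count does not need, and the single-record rule still applies and gives the wrong answer (step 5). The text therefore needs changing on either reading.

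The defence is right that the scope is narrow. The listed endpoint is post-randomization incidence, and its definition does not depend on these windows. The by-visit table is descriptive, with no test or decision attached.

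A reader might also infer that a pre-switch week 12 sample would be shown as week 16. The window limits alone allow it, since day 78 is before day 119, but the documents as a whole do not support it. The by-treatment table covers the Post-randomization Period, which begins at the first dose after randomization, and "Pharmacokinetic and antidrug antibody samples should be drawn prior to investigational product administration at dosing visits". The week 12 sample is therefore lead-in data, and with the period filter a missing week 16 stays empty. It could enter only if windows were assigned before the period filter, or if same-day samples were split by date without time. The SAP prescribes neither. It does not exclude them for ADA either: the footnote on same-day samples in SAP 5.1 names laboratory measurements and belongs to the other table.

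**Conclusion.** The point holds in limited form. As written, the ADA windows and the closest-to-target rule together carry post-randomization results forward into missed visits, in conflict with SAP 8.3. If the table was meant to be cumulative, the rule is unsuitable for ADA. The consequence is confined to the descriptive by-visit ADA table.

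Neither the size nor the direction of the effect can be derived from the documents. It is tempting to apply the planned 15% post-randomization loss to 342 / 2 = 171 subjects per arm, 171 × 0.15 ≈ 26, and to report 26 carried-forward results per arm at late visits. That figure is not supported, for three reasons:

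- The 15% includes subjects who reach week 28 without evaluable PK endpoints, and they may well have late ADA samples.
- Subjects who terminate early are asked for EOS procedures, which include an ADA sample.
- SAP 5.1, read literally, moves subjects who deviate from their regimen into separate actual-treatment groups, outside the two main columns.

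It would also be an inference, not a finding, that late-visit rates are lowered. That assumes ADA positivity rises over time, whereas the SAP allows for transient ADA, so the bias could go either way.

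The conclusion rests on a literal reading of SAP 5.1 and 9.1. The worked cases assume samples on target days, apart from the day 92 EOS example.

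**What to change.** Choose one of two options in SAP 5.1.

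- **(a) Results at each visit.** Give the ADA windows non-overlapping lower bounds: week 6, days 2 to 56; week 12, day 57 to before the first post-randomization dose; week 16, after that dose to day 119; week 20, 120 to 161; week 28, 162 to 196; week 30, 197 to 210; week 32, day 211 onward. Leave missing visits missing. Week 6 should start at day 2. The other table starts it at day 22, which for ADA would leave days 2 to 21 in no window, because there is no week 2 ADA visit.
- **(b) Cumulative incidence.** Label the table as cumulative through each visit, count any positive from the first post-randomization dose to the upper limit, and exempt ADA from the closest-to-target rule.

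Under either option, state that the pre-dose week 12 sample belongs to the Lead-in Period.

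The cost is one SAP edit and one derivation, with no new data. Under (a), by-visit denominators will be smaller at late visits. In the scenarios checked, subjects with complete samples on their target days are assigned to the same visits as before.

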1.3 Schedule of Assessments

Table 1-1. Schedule of Assessments

									We	ek													
	Screen	Baseline	(+ 3 days) (± 3 days)											PK Endpoint Assessments Post Actual Week 28 Dose Date							End of Study (± 3 days) ^a		
Study Visit	≤ 28 days	Week 1/D ay 1	W2/ Day 8	4	6	8	10	12 ^j	14	16	18	20	22	24	26	28 ^b	+1d	+3d	+4d	+7d	+11d	+14d	32
Informed consent	Χ																						
Medical/medication history	Χ																						
Physical examination	Х	Χ																					Х
Height	Χ																						
Weight	Χ	Χ																					Х
Vital signs	Χ	Χ	Χ		Х			Χ		Х		Х				Х						Χ	Х
Adverse events	Xc	Χ	Χ	Х	Х	Χ	Х	Χ	Χ	Х	Χ	Х	Х	Х	Х	Х	Χ	Χ	Х	Χ	Χ	Χ	Х
Concomitant meds	Х	Χ	Х	Х	Х	Х	Х	Χ	Х	Х	Χ	Х	Х	Х	Х	Х	Χ	Х	Х	Χ	Х	Χ	Х
Disease assessments																							
PASI/sPGA/affected BSA	Χ	Χ			Χ			\mathbf{X}^{j}		Х		Χ										Χ	
Laboratory assessments																							
TB Testing ^d	Χ																						
Chest radiography ^e	Χ																						
TB worksheet ^f	Χ																						
Serology (HBsAg, HBcAb, HCV, HIV)	Х																						
Serum pregnancy test	Х																						
Urine pregnancy test		Χ			Х			Χ				Х				Х							Х
Hematology	Χ	Χ			Х			Χ				Х											Х
Chemistry	Х	Χ			Х			Χ				Х											Х
Urinalysis	Х	Χ																					Х
Pharmacokinetic sample ^h		Х			Х			Χ		Х		Χ				Χg	Χ	Χ	Χ	Χ	Χ	Χ	Х
Antidrug antibody sample ^h		Χ			Х			Χ		Х		Χ				Х						Χ	Х
Investigational product																							
Randomization								Χ															
IP administration ⁱ		Χ	Χ	Χ	Х	Х	Х	Χ	Χ	Х	Χ	Х	Х	Χ	Х	Χ							

Clinical Study Protocol: 20200497

Final 1.0 Date: 03 Jun 2021 Page **18** of **87**

BSA = body surface area; CT = computed tomography; HBcAb = hepatitis B core antibody; HBsAg = hepatitis B surface antigen; HCV = hepatitis C virus; HIV = human immunodeficiency virus; IP = investigational product; MRI = magnetic resonance imaging; PASI = Psoriasis Area and Severity Index; PK = pharmacokinetics; PPD = purified protein derivative; sPGA = static Physician's Global Assessment; TB = tuberculosis.

- ^a Subjects terminating early from the study should complete all procedures scheduled for EOS Visit (ie, week 32) within 28 days after withdrawal/discontinuation if possible.
- b Week 28 visit will have a window of ± 3 days.
- ^c Report serious adverse events that occur after signing informed consent form. Nonserious adverse events are reported as medical history prior to enrollment.

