a. The week 28 visit and dose should be performed with a window of ± 3 days. Subsequent visits are done in relation to the actual week 28 investigational product dose date (eg, for the 3 days post week 28 dose time point, the PK sample should be collected 3 days after the actual week 28 dose, with a collection window of ± 6 hours).

Clinical Study Protocol: 20200497

Final 1.0 Date: 03 Jun 2021 Page **19** of **87**

2 Introduction

ABP 501 is Amgen's biosimilar product to Humira[®] (adalimumab). ABP 501 is approved in the United States (US) under brand name of AMJEVITA[™] (adalimumab-atto) and approved/marketed in European Union and other countries, as AMGEVITA[®] (adalimumab). [AMGEVITA[®] Summary of Product Characteristics (SmPC), March 2020, AMJEVITA[™] (adalimumab-atto) United States Prescribing Information (USPI), June 2019]. ABP 501 is approved as a 50 mg/mL formulation.

Amgen is now developing a new ABP 501 high concentration (mg/mL) formulation (referred to in this protocol as ABP 501-HCF). The dosage forms, route of administration (subcutaneous [SC]) and dosing regimens for ABP 501-HCF will be the same as those for the approved 50 mg /mL formulation;

ABP 501-HCF has not been approved or marketed anywhere. For specifics related to the minor differences in excipients between ABP 501 formulations and analytical comparability assessment please refer to the ABP 501 Investigator's Brochure.

Note that in this protocol the term "investigational product" refers to both, ABP 501-HCF or adalimumab (mg/mL approved formulation).

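### The week-30 target moves with the week-28 dose but its window does not, so a week-30 PASI after a dose delayed beyond ±3 days can be filed under week 32 and imputed

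*SAP*

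**What the plan says.** **Analysis visits (SAP 5.1, Study Analysis Visit).** Week 28 has target day 190 and window 162-196. Week 30 has target "14 days post week 28 dose" and window 197-210, and is marked for efficacy. Week 32 is day 211 or later and is not marked for efficacy. The window decides which visit an assessment belongs to. Distance from target matters only when several visits share a window: when more than one "falls within the same defined window, the visit closest to the target day with non-missing data will be considered for analysis". SAP 9.1 makes this derived visit the basis of by-visit summaries unless otherwise noted, and no exception is noted for PASI.

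**Timing (Protocol 1.3).** Footnote b of Table 1-1 says "Week 28 visit will have a window of ± 3 days". Footnote a of Table 1-2 extends this to the dose: "The week 28 visit and dose should be performed with a window of ± 3 days". It adds: "Subsequent visits are done in relation to the actual week 28 investigational product dose date". Footnote i of Table 1-1 says that after an infection or adverse event "the administration of investigational product may be delayed up to 5 days", and that "subsequent doses should be administered according to the original schedule". Table 1-2 allows ±48 hours for the 14-day PK sample. PASI, sPGA and BSA are scheduled at that same visit.

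**Missing data.** SAP 9.6.2.1 imputes a missing week-30 PASI score by LOCF and missing PASI 75/90/100 as non-response. SAP 9.6.3 does the same for week-30 BSA (LOCF) and sPGA response (NRI). The sensitivity analyses in SAP 9.6.2.2 use observed data.

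**The concern.** A target that follows the dose is paired with a window that does not. When the week-28 dose is late, the protocol moves the week-30 visit with it, but the SAP's cut-off stays at day 210. An assessment made when the protocol asks for it can therefore land in a row where efficacy is not analysed.

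What is at stake is a result that was actually collected. Table 1-1 schedules no PASI between week 20 and the 14-day visit, and none at end of study. LOCF would therefore normally reach back to week 20 (day 134), about ten weeks earlier, and NRI would record a failure whatever the subject's true response. The observed-data analyses would not recover the value; they would omit it. A delayed dose is still a received dose, so the subject can stay in the Per-protocol Efficacy Analysis Set unless the delay is classed as an important deviation affecting efficacy. Footnote i delays follow infections or adverse events, so the subjects concerned are not a random sample.

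**Working it through.** **Inputs.** Week-28 target day 190, week-30 window 197-210 and week 32 from day 211 (SAP 5.1). Visit and dose window ±3 days, delay up to 5 days, and ±48 hours at day 14 (Protocol 1.3). The ±48 hours is written for the PK sample; I assume it also describes the efficacy assessments at that visit.

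**The SAP's own figures reproduce.** Target day = (week − 1) × 7 + 1, so week 28 = 27 × 7 + 1 = 190. Week-30 window length = 210 − 197 + 1 = 14 days, as stated. Earlier delays do not accumulate, because later doses return to the original schedule.

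**Week-30 visit day = week-28 dose day + 14, with a tolerance of −2 to +2 days.** The protocol does not say how the 5-day delay relates to the ±3 days, so I take three readings.

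| Reading | Dose days | Week-30 visit days | Combinations on day 211 or later |
|---|---|---|---|
| A. ±3 days limits the dose | 187-193 | 199-209 | 0 of 35 |
| B. Delay of 1-5 days from day 190 | 191-195 | 203-211 | 1 of 25 |
| C. Delay of 5 days from a visit on days 187-193 | 192-198 | 204-214 | 10 of 35 |

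By dose day, the late end looks like this:

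| Dose day | On-time visit | Range | Days falling in week 32 |
|---|---|---|---|
| 194 | 208 | 206-210 | none |
| 195 | 209 | 207-211 | 211 |
| 196 | 210 | 208-212 | 211, 212 |
| 197 | 211 | 209-213 | 211-213 |
| 198 | 212 | 210-214 | 211-214 |

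The thresholds follow directly. An on-time visit is lost when dose day + 14 ≥ 211, that is, from day 197. A visit at the +2-day limit is lost when dose day + 16 ≥ 211, that is, from day 195. At the early end, 187 + 12 = 199, so no visit falls before day 197.

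Over all dose days 187-198, 1 + 2 + 3 + 4 = 10 of 12 × 5 = 60 date combinations are misfiled. This counts calendar possibilities; it is not a share of subjects. With assignment by nominal visit the count is 0 of 60.

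**Size per subject.** The Per-protocol Efficacy Analysis Set has no stated size. With the 15% dropout assumed for PK, 342 × 0.85 / 2 ≈ 145 per arm, and one misfiled responder costs 1/145 ≈ 0.7 percentage points. With all 171 per arm it costs 1/171 ≈ 0.6 points.

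**Week-12 row.** The window is days 57-91 and the target is day 78. Footnote b of the SAP table keeps laboratory values taken after dosing on the week-12 dosing day out of week 12, but says nothing about later days. Suppose the visit and dose fall on day 75 (taking ±3 days to apply) and an unscheduled laboratory test falls on day 81. Both are 3 days from target, and the SAP's tie rule takes the later one, which is after the first post-randomization dose.

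**The case against.** The strongest reply is that Table 1-2 applies the ±3 days to the week-28 dose itself, and SAP 5.1 repeats this. If that limit governs, no compliant week-30 visit is misfiled. Nothing in either document says the two allowances add, so a dose on day 198 comes from stacking them, not from a stated rule. Counting the 5 days from day 190 reaches day 211 only at the edge of the tolerance. This stands, and it limits the point. It does not remove it, because footnote i covers dosing visits generally and makes no exception for week 28.

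A reader might infer that any delayed week-28 dose sends the PASI to week 32. The arithmetic does not support that: a dose up to day 194 is always safe, and one on days 195-196 is safe if the visit is on time.

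A reader might also infer a threat to the trial's main conclusion. There is none. PK samples for weeks 28-30 are summarised by nominal visit, the parameters use actual sampling times (SAP 5.2), and no margin or test rests on the PASI endpoints. Nor do the documents give grounds to expect delays to differ between arms, so a bias in the treatment difference cannot be asserted.

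For week 12, a reader might infer that the reference value is generally contaminated by post-dose data. The closest-to-target rule prevents most of this. A visit on days 78-81 cannot be displaced by a later assessment. Displacement needs an early visit (days 75-77) and an unscheduled assessment at most 6 days later. SAP 9.7.2 describes the shift tables as relative to randomization at week 12, without tying that reference expressly to the window, and half the subjects do not switch at all.

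**Conclusion.** The point holds as a minor defect in the visit-window rule. If the 5-day delay can take the week-28 dose beyond ±3 days, some week-30 PASI, sPGA and BSA values collected on days 211-214 will be imputed or dropped, and no planned week-30 analysis will use them. Doses within ±3 days are unaffected, and so are the primary PK endpoints.

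The conclusion rests on two assumptions: that the delay rule can extend the week-28 dose, which the protocol leaves open, and that the ±48-hour tolerance describes the whole 14-day visit. The number of subjects is probably small but cannot be derived from the documents. The figure of 0.6 to 0.7 points per misfiled responder is an illustration based on assumed arm sizes. The week-12 gap is marginal and is worth closing only because the table is being edited anyway.

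**What to change.** 1. In SAP 5.1, assign week-30 PASI, sPGA and BSA by nominal visit, meaning the 14-day visit after the actual week-28 dose. Keep days 197-210 only for subjects with no week-28 dose or no nominal visit.
2. Reconcile footnote i of Table 1-1 with footnote a of Table 1-2 in the protocol, so that it is clear whether the 5-day delay can take the week-28 dose outside ±3 days. Which should govern is for the sponsor to settle.
3. As a minor addition, restrict the week-12 reference to assessments before the first post-randomization dose, extending footnote b beyond same-day laboratory values.

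The SAP cost is a footnote and a line or two of programming, settled before unblinding. Nominal assignment is cleaner than a wide dose-relative window. One that opened 8 days after a day-187 dose would start on day 195, inside the week-28 row. One that ran to the end-of-study visit would overlap the week-32 row, which vital signs also use. Any dose-relative window would also leave subjects without a week-28 dose unplaced.
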